8.8 Analysis Software

All analyses will be performed using SAS Software version 9.4 or higher.

9. STUDY SUBJECTS

9.1 Disposition of Subjects and Withdrawals

All randomized subjects will be accounted for in this study. If a subject is enrolled but not randomized, the subject will not be included in other analysis tables (apart from the All-Enrolled Set). The numbers and percentages of subjects in each analysis set, study withdrawals, subgroups, and major protocol deviations will be presented by vaccine and overall. Number of subjects per site will be presented by vaccine group and overall for All-Enrolled Set.

The time in days (i.e. date of last assessment minus date of vaccination plus 1) the subjects are under observation for safety will be summarized by vaccine group and overall for Solicited and Unsolicited Safety Sets.

10. DEMOGRAPHICS AND OTHER BASELINE CHARACTERISTICS

In general, all tables related to baseline characteristics should include a Total column across vaccine groups.

10.1 Demographics

Age, height, weight, and body mass index at screening will be summarized by reporting the mean, standard deviation, median, minimum and maximum, and will be calculated by vaccine group and overall.

In addition, the frequency of age categories will be reported as 50-59, and 60-64 years (age cohort). The number and percentages of subjects by sex, country, ethnic origin, race, and previous influenza vaccine history (within the past 3 years) will be presented by vaccine group and overall.

Demographic data will be tabulated for the All-Enrolled Set, FAS Immunogenicity, PPS Immunogenicity, and Overall Safety Set.

10.2 Medical History

The numbers and percentages of subjects with medical history will be presented by Medical Dictionary for Regulatory Activities (MedDRA) system organ class (SOC) and PT by vaccine group and overall. Medical history data will be tabulated for the All-Enrolled Set.

11. IMMUNOGENICITY ANALYSIS

11.1 Blood Samples

For each visit, the number and percentages of subjects with and without blood draws will be summarized overall and by vaccine group. Data will be tabulated for the All-Enrolled Set.

11.2 Primary Objectives Analysis

The primary immunogenicity objectives are:

- 1a. To demonstrate immunological non-inferiority of aQIV versus QIV in subjects 50-64 years of age, as measured by hemagglutination inhibition (HI) geometric mean titers (GMTs) and seroconversion rates (SCR) for each vaccine strain, at 3 weeks after vaccination.
- 1b. To demonstrate that aQIV induces a superior immune response compared to QIV in subjects 50-64 years of age as measured by HI GMTs at 3 weeks after vaccination for at least 2 of the 4 vaccine strains.

Primary Endpoints

Humoral immune responses in terms of HI antibody response against homologous egg-derived vaccine strains (A/H1N1, A/H2N3, B/Yamagata and B/Victoria):

- Geometric Mean Titer (GMT) of HI antibodies at Day 22;
- Seroconversion rate (SCR) defined as the percentage of subjects with either a prevaccination HI (or MN) titer $<1:10$ and a postvaccination (Day 22) HI (or MN) titer $\geq 1:40$, or with a prevaccination HI (or MN) titer $\geq 1:10$ and a ≥ 4 fold increase in post vaccination HI (or MN) titer.

The derived variables are:

- GMT ratios (QIV/aQIV) at Day 22 for each strain.
- The inter-group differences in the SCRs (QIV - aQIV) at Day 22 for each strain.

To evaluate the primary immunogenicity objectives 1a and 1b, the following derived variables of GMT ratios and SCRs differences will be assessed at Day 22:

1a. non-inferiority of aQIV compared to QIV will be assessed for the eight primary endpoints of HI (or MN) geometric mean titer (GMT) and seroconversion rate (SCR) for each virus strain included in the vaccines as follows:

- The GMT ratio (QIV/aQIV) for the A/H1N1 strain
- The GMT ratio (QIV/aQIV) for the A/H3N2 strain

- The GMT ratio (QIV/aQIV) for the B strain (Yamagata lineage)
- The GMT ratio (QIV/aQIV) for the B strain (Victoria lineage)
- The difference between the SCR (QIV-aQIV) for the A/H1N1 strain
- The difference between the SCR (QIV-aQIV) for the A/H3N2 strain
- The difference between the SCR (QIV-aQIV) for the B strain (Yamagata lineage)
- The difference between the SCR (QIV-aQIV) for the B strain (Victoria lineage).

1b. A superior immune response of aQIV compared to QIV will be assessed for the endpoints of HI (or MN) GMT for 2 of the 4 strains included in the vaccines as follows:

- The GMT ratio (QIV/aQIV) for the A/H1N1 strain
- The GMT ratio (QIV/aQIV) for the A/H3N2 strain
- The GMT ratio (QIV/aQIV) for the B strain (Yamagata lineage)
- The GMT ratio (QIV/aQIV) for the B strain (Victoria lineage)

Statistical Hypotheses

Noninferiority of aQIV to QIV (Objective 1a)

To demonstrate that vaccination with aQIV elicits an immune response that is not inferior to that of QIV containing the same virus strains among adults 50-64 years of age, aQIV will be considered to be noninferior to QIV if, for each of the four strains, the following statistical criteria are met:

- The UL of the two-sided 95% CI for the ratio of the Day 22 GMTs (GMTr) does not exceed 1.5. The GMTr will be calculated by GMT_{QIV}/GMT_{aQIV}
- The UL of the two-sided 95% CI for the difference between the SCRs does not exceed 10%. The difference in SCR will be calculated by $SCR_{QIV} - SCR_{aQIV}$

The statistical hypotheses to be tested for the primary immunogenicity objective 1a correspond to:

$H_{0k}: GMTr_k > 1.5$, for any strain k ($k=1,2,3,4$) at Day 22

$H_{ak}: GMTr_k \leq 1.5$, for all strains at Day 22

and

$H_{0(k+4)}: D_k > 10\%$, for any strain k ($k=1,2,3,4$) at Day 22

$H_{a(k+4)}: D_k \leq 10\%$, for all strains at Day 22

where D_k ($k=1,2,3,4$) is the 4 strain-specific Day 22 SCRs differences ($\pi_{QIV,k} - \pi_{aQIV,k}$), namely,

- $D_1 = \pi_{QIV,1} - \pi_{aQIV,1}$ for A/H1N1 strain at Day 22
- $D_2 = \pi_{QIV,2} - \pi_{aQIV,2}$ for A/H3N2 strain at Day 22
- $D_3 = \pi_{QIV,3} - \pi_{aQIV,3}$ for B/Victoria strain at Day 22
- $D_4 = \pi_{QIV,4} - \pi_{aQIV,4}$ for B/Yamagata strain at Day 22

where $\pi_{QIV,k}$, $\pi_{aQIV,k}$ ($k=1,2,3,4$) denotes the seroconversion rates for the four strains in QIV and aQIV respectively.

and $GMTr_k$ ($k=1,2,3,4$) is any of the 4 strain-specific Day 22 GMT ratios, namely,

- $GMTr_1 = \text{GMT}_{QIV}/\text{GMT}_{aQIV}$ for A/H1N1 strain
- $GMTr_2 = \text{GMT}_{QIV}/\text{GMT}_{aQIV}$ for A/H3N2 strain
- $GMTr_3 = \text{GMT}_{QIV}/\text{GMT}_{aQIV}$ for B/Victoria strain
- $GMTr_4 = \text{GMT}_{QIV}/\text{GMT}_{aQIV}$ for B/Yamagata strain.

Translating into \log_{10} transformed GMT titer values, the hypothesis for GMT ratios comparisons become

$$H_{0k}: \mu_{QIV,k} - \mu_{aQIV,k} > \log_{10}(1.5) \text{ for any strain } k (k=1,2,3,4) \text{ at Day 22}$$

$$H_{ak}: \mu_{QIV,k} - \mu_{aQIV,k} \leq \log_{10}(1.5), \text{ for all strains at Day 22.}$$

Where $\mu_{QIV,k}$ and $\mu_{aQIV,k}$ denote the mean of the \log_{10} transformed QIV and aQIV HI titer of the k th strain.

According to the stepwise procedure the following superiority test(s) are only conducted if all above non-inferiority hypotheses can be rejected.

Superiority of aQIV to QIV (Objective 1b)

To demonstrate that aQIV induces a superior immune response compared to QIV in subjects 50-64 years of age as measured by HI GMTs at 3 weeks after vaccination for at least 2 of the 4 vaccine strains. aQIV will be considered to be superior to QIV if the following statistical criteria are met:

- The UL of the two-sided 95% CI for inter-group GMT ratio (QIV/aQIV) < 1.0 for at least 2 of the 4 vaccine strains.

The statistical hypotheses to be tested for the primary immunogenicity objective 1b correspond to:

$$H_{0k}: GMTr_k \geq 1, \text{ for at least 3 of the 4 vaccine strains at Day 22}$$

$$H_{ak}: GMTr_k < 1, \text{ for at least 2 of the 4 vaccine strains at Day 22}$$

where $GMTr_k$ ($k=1,2,3,4$) are defined as above.

Translating into \log_{10} transformed GMT titer values, the hypothesis for GMT ratios comparisons become

$H_{0k}: \mu_{QIV,k} - \mu_{aQIV,k} \geq 0$, for at least 3 out of 4 vaccine strains ($k=1,2,3,4$) at Day 22

$H_{ak}: \mu_{QIV,k} - \mu_{aQIV,k} < 0$, for at least 2 of the 4 vaccine strains at Day 22.

Statistical Models:

Let $\log_{10}(Y_{ijk})$ denote the \log_{10} -transformed HI titer Y_{ijk} . $\log_{10}(Y_{ijk})$ are identical, independent normal distributed random variables, where i denotes the vaccine group aQIV or QIV; $j=1,..,n$ denotes subject j , $k=1, 2, 3, 4$ denotes the four vaccine strains.

$\log_{10}(Y_{ijk}) \sim N(\mu_{ik}, \sigma_{ik}^2)$ with μ_{ik} , and σ_{ik}^2 unknown. μ_{ik} represents mean of the \log_{10} -transformed HI titer level in QIV, aQIV of strain k .

X_{ijk} , $i = \text{aQIV, QIV}$, $j=1,..,n$, $k=1, 2, 3, 4$ independent Bernoulli distributed random variables: $X_{ijk} \sim B(1, \pi_{ik})$, where π_{ik} represents the probability for seroconversion in aQIV, QIV for strain k .

Statistical tests for GMT ratios

HI antibody titers will be \log_{10} transformed and modeled using analysis of covariance with a qualitative factor for vaccine group (η_{ik} , $i = \text{aQIV, QIV}$), age stratum (α_{jk} , $j=1,2$), history of influenza vaccination within the 3 previous seasons (yes/no) (γ_{lk} , $l=1,2$), sex (ξ_{mk}), and a common slope (β) representing the impact of the \log_{10} - prevaccination antibody titer τ_{0ik} , for subject n ,

$$\mu_{ijlmkn} = \lambda_k + \eta_{ik} + \alpha_{jk} + \gamma_{lk} + \xi_{mk} + \beta \tau_{0ik} + \varepsilon_{ijlmkn} \quad (k=1, 2, 3, 4 \text{ strains})$$

where $\varepsilon_{ijlmkn} \sim i.i.d N(0, \sigma_k^2)$. The statistical tests for noninferiority (1a) ($H_0: \mu_{QIV,k} - \mu_{aQIV,k} > \log_{10}(1.5)$), and for superiority(1b) ($H_0: \mu_{QIV,k} - \mu_{aQIV,k} \geq 0$), and translating into adjusted ratios of geometric means and pertaining 2-sided CIs will be calculated based on these models.

Summary statistics will be completed by providing minimum, maximum and median titers for each vaccine group.

Analysis of binary endpoints

Statistical tests for seroconversions

The number and proportion of subjects achieving the binary endpoints (percentage of subjects with seroconversion) will be summarized by assessment (Day 22) and vaccine group, overall.

These summaries will be reported together with the associated two-sided 95% CIs for the proportion according to Clopper-Pearson.

The binary endpoints (percentage of subjects with seroconversion) will be compared between vaccine groups by the differences of proportions with two-sided 95% CI using the Miettinen and Nurminen method ([Miettinen and Nurminen 1985](#)).

Additional supportive analyses may be done using generalized linear models with a qualitative factor for vaccine group, age stratum, history of any influenza vaccination within the 3 previous seasons (yes/no), and sex. Adjusted differences and pertaining 2-sided 95% CI between vaccine groups will be calculated based on the model.

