8.4.2.3.3 Statistical Methods

All statistical analyses for HI (or MN if applicable) titers will be performed on the logarithmically (base 10) transformed values. Individual HI titers below the detection limit (<10) will be set to half of that limit (5); values above the upper limit of quantification will be set to the upper limit.

Reverse cumulative distribution curves will be derived by time-point and strain.

Crude estimates for GMTs, GMFIs, and pertaining 2-sided 95% CIs will be calculated assuming a log-normal distribution of the titers and will be completed by providing minimum, maximum and median titers for each treatment group. Binary data (i.e., percentages of subjects with seroconversion and with titer $\geq 1:40$) will be summarized for each group using crude estimates and will be reported together with 2-sided 95% CIs calculated according to Clopper's and Pearson's method ([Clopper and Pearson 1934](#)). No multiplicity adjustment to the CI levels will be implemented.

The analysis model for the HI GMT will use a general linear model on log-transformed (base 10) Day 22 titers as the outcome variable and as covariates: treatment groups (aQIV, and QIV), prevaccination titer (\log_{10} transformed), age stratum, gender, and history of any influenza vaccination within the 3 previous influenza seasons. From this model, adjusted differences in the least square means (on the \log_{10} scale) will be produced with 95% confidence limits for QIV versus aQIV. The estimated difference and the confidence limits will be back-transformed to obtain *adjusted GMT ratios* with 95% confidence limits. The adjusted GMT ratio will be the result for which the assessment of the HI GMT primary endpoint will be based on. Each of the 4 strains will be analyzed separately.

Potential covariate interaction effects will also be examined in the fit of the GLM, as well as the other co-variates such as age taken as a continuous factor.

The differences of binary endpoints (i.e. seroconversion or titer $\geq 1:40$) will be compared using the Miettinen and Nurminen method ([Miettinen and Nurminen 1985](#)). Additional supportive analyses might be done using generalized linear models with factors for treatment group, age subgroup, prevaccination titer (\log_{10} transformed) as well as vaccination history. Adjusted differences between treatment groups with 2-sided 95% CI will be calculated based on the model and potential interaction effects will be examined.

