8.1 Adjustment for Covariates

The main statistical analysis includes descriptive statistics for the overall population. Subgroup analyses will be done by age cohort (50-59 and 60-64 year of age), previous vaccination history, sex, race, ethnicity, and comorbidity risk scores (Hak score, <50 and ≥ 50). Summary tables will show unadjusted GMTs for each vaccine group by time point.

Adjusted GMTs will be calculated based on the \log_{10} -transformed antibody titers at Day 22/181/271 using an ANCOVA model which includes the vaccine group (aQIV and QIV), \log_{10} -transformed pre-vaccination antibody titer, age cohort (50-59 or 60-64 year of age), sex, and history of any influenza vaccination within the 3 previous seasons (yes/no). The main analysis of binary immunogenicity endpoints (i.e., percentages of subjects with seroconversion) will not be adjusted for any of the covariates. Binary data will be summarized for each group using unadjusted estimates and will be reported together with two-sided 95% CIs calculated according to the Clopper-Pearson method. Sensitivity analysis may be done to include the vaccine group (aQIV and QIV), stratification factors age and previous vaccination history, and sex in a generalized linear model

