8.5 Subgroups

Adjusted (same model as the main analysis by subgroup with subgroup factor removed if it is in the main model) and unadjusted immunogenicity analysis of the GMTs and SCRs will be performed by stratifying for the following subgroups:

- Age cohort (50-59 and 60-64 years of age)
- Previous vaccination history (Yes and No)
- Sex
- Race
- Ethnicity
- Comorbidity risk score (<50 and ≥ 50)

Safety analysis will be performed by stratifying for the following subgroups:

- Age cohort (50-59 and 60-64 years of age)
- Previous vaccination history (Yes and No)
- Sex
- Race
- Ethnicity
- Comorbidity risk score (<50 and ≥ 50)

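### The SAP's optional adjusted model for seroconversion omits the prevaccination titer that the protocol lists, gives no reason, and leaves the adjusted subgroup model for SCR undefined

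*SAP*

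**What the plan says.** **Main SCR analysis.** SAP 8.1 says the main analysis of binary endpoints "will not be adjusted for any of the covariates". SAP 11.2 compares the groups by "differences of proportions with two-sided 95% CI using the Miettinen and Nurminen method". The protocol uses the same method. This comparison decides the SCR part of objective 1a.

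**Supportive adjusted model, protocol.** Section 8.4.2.3.3 says further analyses might use "generalized linear models with factors for treatment group, age subgroup, prevaccination titer" (log10 scale), together with vaccination history. Sex is not listed.

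**Supportive adjusted model, SAP.** Section 11.2 says: "Additional supportive analyses may be done using generalized linear models with a qualitative factor for vaccine group, age stratum, history of any influenza vaccination"; the list ends with sex. Section 8.1 says: "Sensitivity analysis may be done to include the vaccine group (aQIV and QIV), stratification factors age and previous vaccination history, and sex". Neither lists the prevaccination titer. SAP section 1 states that the plan is based on protocol version 3.0 of 11 July 2022, which is the version that lists it.

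**Subgroups.** The sentence in SAP 8.5 opens with an adjusted analysis that takes the same model as the main analysis, minus the subgroup factor if that factor is in it. It continues with "unadjusted immunogenicity analysis of the GMTs and SCRs will be performed" for six subgroup variables.

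**Use of the titer elsewhere.** SAP 8.7 defines seroconversion from the Day 1 titer. The SAP's GMT model (8.1 and 11.2) includes log10 prevaccination titer as a covariate.

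**The concern.** Two documents prescribe different models for the same analysis, and the later one does not say why. The covariate removed is the one built into the endpoint. Under SAP 8.7, values below 1:10 are set to 5, so a subject below the limit needs a recorded 8-fold rise (5 to 40), while a subject at 1:10 needs a 4-fold rise (10 to 40) and one at 1:160 needs 1:640. The chance of seroconverting can therefore be expected to vary with the starting titer, even though each subject is compared with his or her own baseline.

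An adjusted SCR difference without that covariate gives up whatever precision the titer would bring, and does not correct a chance difference between arms in Day 1 titer. Such differences tend to be larger in small subgroups. Separately, a programmer working from SAP 8.5 cannot tell whether an adjusted SCR subgroup analysis is wanted or which model to fit, so the choice could end up being made after the data are seen.

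**Working it through.** **1. Covariate lists side by side**

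| Term | Protocol 8.4.2.3.3, SCR model | SAP 8.1, SCR model | SAP 11.2, SCR model | SAP GMT model |
|---|---|---|---|---|
| Vaccine group | yes | yes | yes | yes |
| Age stratum | yes | yes | yes | yes |
| Vaccination history | yes | yes | yes | yes |
| log10 prevaccination titer | **yes** | **no** | **no** | yes |
| Sex | no | yes | yes | yes |
| Status | might | may | may | main analysis |

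The omission occurs in both SAP sections.

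**2. The plan's own SCR power figure**

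Inputs from SAP section 5: 1,816 evaluable subjects (908 per arm), margin 10 points, one-sided alpha 0.025, and the assumed SCRs in Table 3. With SE = √[(pA(1−pA) + pQ(1−pQ))/908], power is Φ[(0.10 − (pQ − pA))/SE − 1.96]. The number per arm for 90% power is (1.96 + 1.2816)² × [pA(1−pA) + pQ(1−pQ)] / (0.10 − (pQ − pA))².

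| Strain | aQIV / QIV | SE | Power | n per arm for 90% |
|---|---|---|---|---|
| A/H1N1 | 86% / 76% | 0.0183 | >99.99% | 80 |
| A/H3N2 | 87% / 77% | 0.0179 | >99.99% | 77 |
| B | 82% / 80% | 0.0184 | 99.9997% | 225 |

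For B: SE = √[(0.1476 + 0.1600)/908] = 0.0184, and 0.12/0.0184 − 1.96 = 4.56. The stated ~100% is reproduced. It belongs to the unadjusted test and does not depend on this covariate.

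**3. What the titer could add (illustration on assumptions)**

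The documents give neither the baseline titer distribution nor its association with seroconversion. The illustration takes the B strain (82% against 80%, 908 per arm), a normally distributed baseline log10 titer, and an assumed log-odds slope per SD of that titer. A logistic model with group and titer was standardised to a risk difference, because both documents ask for adjusted differences. There were 1,500 simulated trials per slope. The SE cut is 1 − √(variance ratio).

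| Assumed slope per SD | SE unadjusted (points) | SE adjusted (points) | Variance ratio | SE cut | SD of adjusted minus unadjusted (points) |
|---|---|---|---|---|---|
| 0 | 1.85 | 1.85 | 1.000 | 0% | 0.04 |
| −0.5 | 1.82 | 1.80 | 0.978 | 1.1% | 0.35 |
| −1.0 | 1.84 | 1.74 | 0.894 | 5.4% | 0.67 |
| −1.5 | 1.84 | 1.61 | 0.764 | 12.6% | 0.88 |
| −2.0 | 1.83 | 1.52 | 0.696 | 16.6% | 1.05 |

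The mean estimate is about −2 points with and without the titer in every row, and noninferiority power stays at ~100%. The last column shows how far adjustment typically moves a single trial's estimate.

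A rough cross-check for a linear term is an SE ratio of √(1 − r²), where r is the correlation of seroconversion with baseline titer. An assumed r of −0.1 gives √0.99 = 0.995, a cut of 0.5%. An assumed r of −0.4 gives √0.84 = 0.917, a cut of 8.3%.

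The simulation compares titer adjustment with no adjustment. Against the SAP's own model the gain may be smaller, because vaccination history could already carry some of the baseline information.

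**4. SAP 8.5 read against SAP 8.1**

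The subgroup section takes its adjusted model from the main analysis. For GMT that model exists and contains the titer. For SCR there is none, because the main SCR analysis is unadjusted. Either adjusted applies to GMT only, or it means the optional SCR model without the titer. The text settles neither.

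**The case against.** The strongest reply is that this model decides nothing. Both documents make it optional, and the SCR criterion rests on the unadjusted Miettinen–Nurminen difference. That stands in full.

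The protocol also leaves statistical detail to the SAP (8.1 and 8.4.2.3.3), so changing an optional model is arguably within that delegation. This stands in part: it permits a change but does not explain why a listed covariate was removed and another added.

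Baseline titer is also handled elsewhere. It is in the GMT model, seroconversion is measured against each subject's own Day 1 value, and randomization is stratified by age and vaccination history, both of which are in the SAP's SCR model. This reduces the likely gain but does not make it zero.

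A reader might infer from SAP 8.5 that adjusted SCR analyses without the titer are compulsory. The documents do not support this. The reference to the main-analysis model fits GMT, and a natural reading is adjusted and unadjusted GMTs with unadjusted SCRs. The section is ambiguous; it is not a clear mandate.

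**Conclusion.** The mismatch between protocol and SAP is confirmed, is unexplained, and appears in both SAP sections that describe the SCR model. The gap in SAP 8.5 is confirmed as an ambiguity. Both are worth correcting, but the consequences are limited to supportive SCR estimates and any adjusted subgroup SCR estimates.

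A reader might infer that the primary SCR noninferiority result is biased or underpowered. It is not: that test uses no covariates, its power is ~100%, and randomization means that leaving out a baseline covariate causes no systematic bias.

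The size of the precision loss cannot be fixed from the documents. Under the assumed slopes, the SE cut from including the titer runs from none to about 16–17% against an unadjusted estimate. The upper end needs a strong association, and a weak one gives almost nothing. A reader might also take the protocol to require a nonlinear titer term or a mandatory adjusted analysis. It lists a single log10 term in an analysis that might be done.

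**What to change.** - In SAP 8.1 and 11.2, add log10 prevaccination titer to the generalized linear model for seroconversion, as in protocol 8.4.2.3.3. Sex may stay, with a line noting that it goes beyond the protocol's list.
- In SAP 8.5, state that this is the model for any adjusted SCR subgroup analysis, with the subgroup factor removed where it is in the model.

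Optional extras that the protocol does not require: a nonlinear term or a below/above 1:10 indicator, since the seroconversion rule changes at that titer, and a commitment to report the adjusted analysis for all four strains.

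The cost is one covariate in a model already described and two or three lines of text. The Day 1 titer is already needed to derive seroconversion, so no new data are required, and sample size, alpha and the primary test stay as they are.
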